## **Abbreviations**

AF	Atrial Fibrillation
CABG	Coronary Artery Bypass Grafting
CI	Claudicatio Intermittens
PAOD	Peripheral Artery Occlusive Disease

## 1 Scientific Background

Nearly 30% of patients undergoing coronary artery bypass grafting (CABG), 40% of patients undergoing valvular heart surgery and over 50% of patients with combined coronary and valvular procedures develop atrial fibrillation (AF) [1].

Postoperative AF occurs mostly due to conditions like chronic kidney diseases, emergency surgery, age >75 years, cardiopulmonary bypass time >180 min and due to lacking postoperative application of aldosterone- and beta-blockers [2].

An overview of pre- intra- and postoperative risks for AF is listed in Table 1: Pre-, intra-, postoperative risks for AF [1].

Preoperative	Intraoperative	Postoperative
High age	Endotracheal tube insertion	Return to intensive care unit
Male gender	Intraoperative IABP	Ventilation longer than 24 hours
Previous cardiac surgery	Left ventricular venting	Volume overload
Valvular heart disease	Aortic cross-clamp time	Pneumonia
Chronic lung disease	Extracorporeal circulation	Electrolyte imbalances
Chronic renal failure	Myocardial ischemia	Imbalance of auton. nervous system
Left atrium enlargement	Venous cannulation	Atrial extrasystole
Left ventricular hypertrophy	Damage to the atrium	Increased postop adrenergic status
Withdrawal of beta-blocker medication	Excess inotropic requirements	Increased afterload
History of AF Hypertension	Acute volume change	Inflammation
Obesity		Hypotension
Diabetes		
Metabolic syndrome		

**Table 1: Pre-, intra-, postoperative risks for AF [1]**

Several theories describe the emergence of AF like “multiple-wavelet re-entry”, “focal mechanism” and “mother rotor” but the exact underlying mechanisms are still not well understood [1].

Prevention and treatment of postoperative AF are managed with conservative medication therapies including e.g. beta-blockers and other clinical interventions include radio frequency catheter ablation, cardioversion and occlusion of the left atrial appendage [3].

A novel approach for suppression of AF utilizing low-level transcutaneous electrical vagus nerve stimulation has been described recently in the Journal of the American College of Cardiology [4]. The newly developed “DUCEST Neurostimulator V” device (manufactured by Biegler Medizinelektronik GmbH Mauerbach, Austria) offers similar action as in [4]. This Neurostimulator device is designed to emit small direct current electrical pulses (0-1,2mA) to stimulate the R.auricularis of the vagus nerve located at the Fossa triangularis. The target population are patients with de-novo postoperative AF. The stimulation is achieved with the attachment of two needle-electrodes and connection of the electrodes to the Neurostimulator.

Following the stimulation of the vagus nerve positive effects were already achieved in chronical wound healing, peripheral artery occlusive disease (PAOD), Claudicatio intermittens (CI) and chronic pain patients [5][6][7][8].

## **2 Aim of the project**

The current study will evaluate the potential of stimulating the R.auricularis of the vagus nerve located at the Fossa triangularis to ameliorate or suppress AF in the study population.

## **3 Study population**

The target population are patients with de-novo postoperative AF who underwent bypass operation and/or aortic valve replacement.

### **3.1 Inclusion Criteria**

- De-novo postoperative AF
- CABG or aortic valve replacement
- Age of 18-80 years
- Willing and able to understand, sign and date the informed consent form that has been approved by the institutional review board

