## **4 Methods**

Patients are randomized to a treatment or a sham group. The corresponding device is prepared by a third person according to the double-blind setting for the surgeon. The DUCEST Neurostimulator V needle-electrodes are applied post-operatively to stimulate the R.auricularis of the vagus nerve located at the Fossa triangularis. Connecting the needle-electrode cables to the Neurostimulator V activates the device. (The stimulation intensity can be adjusted from 0,05mA to 1,2mA, default value is 0,4mA). The starting stimulation intensity will be adjusted to 1mA and takes place at 1Hz continuously for 40 minutes, followed by a 20 minute break. The built-in 3V battery lasts for approx. 14 days. After 7 days the electrodes are replaced and applied to the other ear of the patient. A plaster with a plastic mounting clip is attached on the shoulder of the patient. The Neurostimulator is connected to the mounting clip. After 14 days or at hospital discharge of the patient, the device is unmounted and the needle-electrodes are removed.

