## **7 Investigational Procedure**

Patients will be randomized double-blind into a treatment and sham group. Each group will consist of 20 Patients (please see "9 Statistical Analysis"). The follow-up covers the post-op hospital stay (approx 7-14 days). Inflammation markers will be assessed at day 0 (at device attachment), +2 and +7 days post device attachment. CRP, TNF-alpha, IL-6, and IL-10 will be assessed. Safety measures will include screening for and treatment of any occurring adverse events, vital signs, physical examination, ECG, 24-hour continuous ambulatory ECG, heart rate variability, laboratory safety tests, infection assessment, inflammation screen. In the event of procedure-related cardiac arrhythmias, ACC/AHA/ESC 2006 Practice Guidelines for management of subjects with ventricular arrhythmias and the prevention of sudden cardiac death will be implemented.

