## 9 Statistical Analysis

### Power and sample size calculation

Two-sample test to determine whether the mean in group A,  $\mu_A$ , is different from the mean in group B,  $\mu_B$ . The hypotheses are

$$H_0: \mu_A - \mu_B = 0$$

$$H_1: \mu_A - \mu_B \neq 0.$$

Where the ratio between the sample sizes of the two groups is  $\kappa = n_A/n_B$

Formulas to compute sample size and power, respectively:

$$n_A = \kappa n_B \text{ and } n_B = (1 + 1/\kappa) * (\sigma^2 (z_{1-\alpha/2} + z_{1-\beta}) / (\mu_A - \mu_B))^2$$

$$1 - \beta = \Phi(z - z_{1-\alpha/2}) + \Phi(-z - z_{1-\alpha/2}), \quad z = (\mu_A - \mu_B) / (\sigma \sqrt{1/n_A + 1/n_B})$$

where

$\kappa = n_A/n_B$  is the matching ratio

$\sigma$  is standard deviation

$\Phi$  is the standard Normal distribution function

$\Phi^{-1}$  is the standard Normal quantile function

$\alpha$  is Type I error

$\beta$  is Type II error, meaning  $1 - \beta$  is power

utilizing the values:

Group 'A' mean,  $\mu_A = 20$  (estimates for mean TNF- $\alpha$  in pg/ml in treatment group)

Group 'B' mean,  $\mu_B = 30$  (estimates for mean TNF- $\alpha$  in pg/ml in sham group)

Standard Deviation,  $\sigma = 10$  (estimates for TNF- $\alpha$  standard deviation)

Sampling Size  $n_A = 20$  (treatment group size)

Sampling Size  $n_B = 20$  (sham group size)

Sampling Ratio,  $\kappa = n_A/n_B = 1$

Type I error,  $\alpha = 0,05$

calculates the Power,  $1-\beta = 0,8859$  which is an acceptable value.

For the statistical evaluation of the study data the software Graphpad Prism will be used. The evaluation of the double-blind data will be performed by a competent person utilizing appropriate statistical measures.

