## **10 Randomization**

The randomization procedure will be conducted utilizing the MUW randomizer (<https://www.meduniwien.ac.at/randomizer>) to achieve a 50% / 50% assignment of patients to the treatment and the sham group.

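### Marker samples are timed from device attachment with no fixed interval from surgery, and the stated paired t-tests neither compare the arms nor allow for this

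*Protocol*

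**What the plan says.** Section 3.1 requires "De-novo postoperative AF" and, as the surgical criterion, "CABG or aortic valve replacement". Neither 3.1 nor 3.2 gives a minimum or maximum time from the operation to AF onset, randomisation or attachment. Section 4 says only that the "needle-electrodes are applied post-operatively to stimulate the R.auricularis".

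Section 7 sets the sampling clock: "Inflammation markers will be assessed at day 0 (at device attachment), +2 and +7 days post device attachment". The only indirect bound on timing is the hospital stay. Section 7 runs follow-up over a post-operative stay of roughly 7 to 14 days, and section 4 adds: "After 14 days or at hospital discharge of the patient, the device is unmounted".

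In section 9 the sample size rests on a two-sample comparison of mean TNF-alpha: 20 v 30 pg/ml, SD 10, 20 patients per arm, two-sided alpha 0.05, stated power 0.8859. The SD is described only as "estimates for TNF- $\alpha$ standard deviation", with no source and no sampling day. Under Secondary Endpoint the same section lists IL-6, IL-10, CRP and TNF-alpha and names paired t-tests as the method. Section 10 aims "to achieve a 50% / 50% assignment of patients to the treatment and the sham group" and names no stratification factor.

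**The concern.** AF onset triggers entry, so time since surgery can differ between patients who all carry the label day 0. If the markers move with time since surgery, the samples at 0, +2 and +7 mix different stages of that course. Table 1 of the protocol lists inflammation as a post-operative risk for AF but gives no time course for any marker, so this movement is an assumption.

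Two things would then be at stake. Between-patient variance would rise, and with 20 per arm the arms could differ by chance in time since surgery. A paired t-test answers neither. It asks whether a marker changed from one sample to another in the same patients, and after surgery the answer may be yes in both arms whatever the device does.

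**Working it through.** **1. The plan's own figure.** Inputs from section 9: difference 10, SD 10, n = 20 per arm, alpha 0.05.

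- z = 10 / (10 × √(1/20 + 1/20)) = 10 / 3.162 = 3.162
- Power = Φ(3.162 − 1.960) + Φ(−3.162 − 1.960) = 0.885

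This agrees with the stated 0.8859. An exact two-sample t-test gives 0.869. The figure is for a comparison between arms.

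**2. How far entry can spread.** For the +7 sample to fall within a 14-day stay, attachment must come by about post-operative day 7. If entry were uniform over days 0 to 7 (an assumption), its SD would be 7/√12 = 2.02 days. The standard error of the difference between arms in mean attachment day is 2.02 × √(2/20) = 0.64 days. By chance the arms would differ by more than 1.96 × 0.64 = 1.25 days in about 5% of randomisations.

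**3. Raw levels.** Suppose timing adds an independent SD of e pg/ml and the planned SD of 10 excludes it. Then SD = √(10² + e²), and the plan's formula gives:

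| e (assumed) | SD | Power |
|---|---|---|
| 0 | 10.00 | 0.885 |
| 2 | 10.20 | 0.873 |
| 5 | 11.18 | 0.807 |
| 10 | 14.14 | 0.609 |

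Power reaches 0.80 at an SD of 11.29, that is e = 5.2. The protocol gives no value for e. These figures describe only a two-sample comparison of unadjusted levels, not the paired analysis that the protocol names.

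**4. Within-patient change.** Let d be the post-operative day at attachment.

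- Linear course, Y = a + b × d: change to +2 is 2b and change to +7 is 7b for every patient. The day d drops out, so timing adds no variance.
- Curved course, Y = a + b × d + c × d²: change to +2 is 2b + c(4d + 4), and change to +7 is 7b + c(14d + 49). Now d matters, with added SD 4|c|s and 14|c|s, where s is the SD of d. The protocol gives no c.

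**5. What the paired tests compare.** Section 9 states the null hypothesis as a zero difference between the two arm means. The patients in the two arms are different people and no matching is defined, so a paired t-test can only be run within patients. If it is run in each arm and the results are set side by side, let p be the chance that either arm alone is significant when the device does nothing. Exactly one arm is then significant with probability 2p(1 − p). With no natural change, p = 0.05 and this is 2 × 0.05 × 0.95 = 0.095. With a natural change it can rise to one half, at p = 0.5.

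**The case against.** The strongest case against is that nothing in the protocol shows a loss. The SD of 10 has no stated source and may already come from patients sampled at mixed times, in which case step 3 costs nothing. Under a linear course, pairing removes the timing effect completely. Randomisation makes any imbalance a matter of chance, which a valid between-arm test already allows for. Counting from attachment is a sensible way to measure response to stimulation. The markers are secondary, and no effect on the primary endpoint, AF in routine ECG, is shown. Covariate choice is commonly left to the SAP. All of this stands.

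A reader might go further and infer that the marker comparison is noisier than planned, with a large loss of power. A TNF-alpha slope of 4 pg/ml per day with an attachment-day SD of 3 days would give an SD of √(10² + 12²) = 15.6 and power of 0.526. The documents support neither input. That slope moves TNF-alpha by 28 pg/ml in 7 days against a planned sham mean of 30, the timing SD of 12 exceeds the whole planned SD, and step 2 puts the spread nearer 2 days.

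The objection does not reach the choice of test. The protocol itself fixes paired t-tests, and these do not address the between-arm hypothesis in the same section. Pairing also leaves timing in the change scores if the course is curved.

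**Conclusion.** The point holds in a limited form. Time from surgery to attachment is open, the marker clock starts at attachment, and the named analysis neither compares the randomised arms nor takes account of time since surgery. Timing may add variance and chance imbalance at 20 per arm. Its size is unknown and may be nil: it depends on whether the SD of 10 already includes timing variation and on whether the marker course is curved.

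Two stronger conclusions might be drawn and should not be. One is systematic bias between the arms, which 1:1 randomisation rules out as an effect of entry timing. The other is that eligibility must carry a maximum interval from surgery. That would trade late-onset patients for uniform timing on a secondary endpoint, and the documents do not settle the trade.

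This is a low-cost improvement to the secondary analysis. It carries some extra weight because TNF-alpha is the variable on which the sample size rests.

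**What to change.** In section 9, Secondary Endpoint, replace the paired t-tests with text such as:

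*Each marker at day +2 and at day +7 will be compared between the treatment and sham arms by analysis of covariance, with arm as factor and with the marker's day-0 value and the post-operative day at device attachment as covariates. The adjusted difference between arms will be reported with its 95% confidence interval.*

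Define post-operative day at attachment as attachment date minus surgery date, and add it to the recorded data. The protocol does not list it, but it follows from those two dates.

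The cost is small. No visit, sample or patient is added. With 40 patients and four fitted terms (intercept, arm, two covariates), 36 residual degrees of freedom remain, against 38 for a plain two-sample t-test. The sponsor should confirm that the software named in section 9 will fit the model. No change to eligibility is needed for this.

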### **3.2 Exclusion Criteria**

- Pacemaker or ICD
- Impaired EF < 30%
- Patients with acute myocardial infarction within the past 14 days
- Pregnant or lactating patients
- Any condition that, in the judgement of the investigator, would place the patient at undue risk
- Any concurrent disease or condition that, in the opinion of the investigator, would make the subject unsuitable for participation in the study
- Treatment and/or an uncompleted follow-up treatment of any investigational therapy within 6 months before procedure and intent to participate in any other investigational drug or cell therapy study during the follow-up period of this study
- Active participation in other research therapy for cardiovascular repair/regeneration

## **4 Methods**

Patients are randomized to a treatment or a sham group. The corresponding device is prepared by a third person according to the double-blind setting for the surgeon. The DUCEST Neurostimulator V needle-electrodes are applied post-operatively to stimulate the R.auricularis of the vagus nerve located at the Fossa triangularis. Connecting the needle-electrode cables to the Neurostimulator V activates the device. (The stimulation intensity can be adjusted from 0,05mA to 1,2mA, default value is 0,4mA). The starting stimulation intensity will be adjusted to 1mA and takes place at 1Hz continuously for 40 minutes, followed by a 20 minute break. The built-in 3V battery lasts for approx. 14 days. After 7 days the electrodes are replaced and applied to the other ear of the patient. A plaster with a plastic mounting clip is attached on the shoulder of the patient. The Neurostimulator is connected to the mounting clip. After 14 days or at hospital discharge of the patient, the device is unmounted and the needle-electrodes are removed.

## **5 Benefit of study**

Postoperative AF is a significant morbidity in cardiac surgery which is associated with decreased survival in the long term. Even a slight decrease in postoperative AF is highly desirable. Our goal is to evaluate if the DUCEST Neurostimulator V is a safe and effective alternative to current treatment options for AF.

## **6 Risk of study**

Possible local inflammation at needle-electrodes during prolonged use (>7d)

## **7 Investigational Procedure**

Patients will be randomized double-blind into a treatment and sham group. Each group will consist of 20 Patients (please see "9 Statistical Analysis"). The follow-up covers the post-op hospital stay (approx 7-14 days). Inflammation markers will be assessed at day 0 (at device attachment), +2 and +7 days post device attachment. CRP, TNF-alpha, IL-6, and IL-10 will be assessed. Safety measures will include screening for and treatment of any occurring adverse events, vital signs, physical examination, ECG, 24-hour continuous ambulatory ECG, heart rate variability, laboratory safety tests, infection assessment, inflammation screen. In the event of procedure-related cardiac arrhythmias, ACC/AHA/ESC 2006 Practice Guidelines for management of subjects with ventricular arrhythmias and the prevention of sudden cardiac death will be implemented.

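### The +7-day marker sample is timed from device attachment but follow-up ends at discharge, so early-discharged patients will lack it, and the 20 v 20 TNF-alpha calculation names no day and allows for no loss

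*Protocol*

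**What the plan says.** Two clocks run in the protocol.

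- **Follow-up and treatment.** Section 7: "The follow-up covers the post-op hospital stay (approx 7-14 days". Section 4: "After 14 days or at hospital discharge of the patient, the device is unmounted and the needle-electrodes are removed".
- **Marker sampling.** Section 7 takes inflammation markers at day 0, when the device goes on, and at +"2 and +7 days post device attachment".

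Attachment is later than surgery. Section 3.1 requires "De-novo postoperative AF" for entry, and section 4 says the "needle-electrodes are applied post-operatively to stimulate the R.auricularis". No postoperative day is fixed for it.

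On numbers, section 7 says "Each group will consist of 20 Patients" and refers to section 9. There the power calculation takes 20 as the "treatment group size" and 20 for sham, with TNF-alpha means of 20 and 30 pg/ml, SD 10 and alpha 0.05, and reports power 0.8859. It does not say on which day those means apply. The markers are the secondary endpoint, to be analysed with paired t-tests.

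**The concern.** If a patient's device is attached k days after surgery, the last marker sample is due on postoperative day 7 + k. At the short end of the stated stay, any k above zero puts that sample after discharge, when follow-up is over and the device is off. The protocol has no visit after discharge and no substitute sample at discharge.

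Two things are at stake in the marker analysis. The first is precision: fewer than 20 per arm may have a +7 value, and a paired test that includes +7 needs both members of the pair. The second is selection: values are lost through early discharge, which plausibly goes with faster recovery, so the patients who remain at +7 may be the slower-recovering ones.

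**Working it through.** **Inputs from the protocol (section 9):** means 20 and 30 pg/ml, so a difference of 10; SD 10; two-sided alpha 0.05; 20 per arm; stated power 0.8859. From section 7: stay about 7-14 days.

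**Step 1, reproduce the stated power.** The protocol's formula is 1 − β = Φ(z − 1.96) + Φ(−z − 1.96), with z = difference / (SD × √(1/n + 1/n)). Here z = 10 / (10 × √(2/n)) = √(n/2). For n = 20, z = 3.162 and Φ(1.202) = 0.8854; the second term is negligible. The stated 0.8859 is reproduced to within 0.001. The exact two-sample t-test (noncentral t) gives 0.869 at the same n.

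**Step 2, how many +7 values might be lost.** The protocol gives neither the attachment day nor the distribution of stay, so this step is an assumption: stay uniform over 7-14 days, attachment on postoperative day k. The share discharged before day 7 + k is k/7.

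- k = 1: 14% lost; 20 × 6/7 = 17.1, about 17 per arm
- k = 2: 29% lost; 20 × 5/7 = 14.3, about 14 per arm
- k = 3: 43% lost; 20 × 4/7 = 11.4, about 11 per arm

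If stay is instead a whole number of days, equally likely from 7 to 14, and a sample may be taken on the day of discharge, the share is k/8: 12.5%, 25% and 37.5%. A distribution weighted to longer stays would lose fewer, and one weighted to shorter stays more.

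**Step 3, power at +7 for the evaluable number, each method against its own baseline.**

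| Evaluable per arm | z = √(n/2) | Protocol's formula | t-test |
|---|---|---|---|
| 20 | 3.162 | 0.885 | 0.869 |
| 17 | 2.915 | 0.830 | 0.807 |
| 16 | 2.828 | 0.807 | 0.781 |
| 15 | 2.739 | 0.782 | 0.753 |
| 14 | 2.646 | 0.754 | 0.721 |
| 11 | 2.345 | 0.650 | 0.607 |

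Power goes below 0.80 at 15 per arm (25% missing) by the protocol's formula, and at 16 per arm (20% missing) by the t-test.

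**Step 4, the same check for +2.** With the shortest stated stay of 7 days, a +2 sample falls within the stay whenever attachment is on postoperative day 5 or earlier (5 + 2 = 7). Few +2 values should therefore be missing.

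**The case against.** A reader might infer that the trial cannot reach 20 v 20, or that its stated power is wrong. The protocol does not support that. It gives no attachment day and no distribution of stay. Patients who stay towards 14 days can have a +7 value, and section 4 moves the electrodes to the other ear after 7 days, so some patients are expected to be in hospital that long. Section 9 ties the TNF-alpha means to no day; if the comparison meant is at +2, most of the shortfall disappears. Setting t-test power against the stated 0.8859 would also exaggerate the fall, because the t-test gives 0.869 with nobody missing. All of this stands.

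A reader might also infer that the comparison between arms is biased. That would need loss, or its relation to marker level, to differ between arms, and the protocol shows neither. Selective loss is a risk here, not a demonstrated bias.

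It is also fair that missing-data rules and the details of a secondary model are commonly left to an SAP, which may exist. Their absence is not the point. The sampling schedule and the follow-up window are fixed in this protocol, in adjacent sentences, and do not fit together for part of the stated range of stay. An SAP can handle missing samples but cannot recover them.

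**Conclusion.** The point holds in limited form. Any patient discharged before attachment +7 will have no +7 marker value, the loss may be related to recovery, and the 20 v 20 calculation names no day and makes no allowance for it.

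The size is conditional. Only if the powered comparison is at +7, and under the assumed uniform stay with attachment on day 1, 2 or 3, does power fall to the 17, 14 and 11 per arm rows of the table. The thresholds at which power drops below 0.80 do not depend on the assumed stay, but how many patients are lost does. The primary endpoint, AF in routine ECG, does not use these samples and is not affected. The change is worth making before recruitment because it is cheap and a missed sample cannot be replaced.

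**What to change.** 1. **Reconcile the sampling clock with the follow-up window.** Take the last blood sample at +7, or at discharge if that is earlier, and record the actual sampling day.
2. **Name the day to which the TNF-alpha power applies**, for example +2, and restate power for the number of patients expected to have a value on that day. If +7 is preferred, keeping 20 evaluable per arm needs 20 / (1 − d) patients: 23 at 10% missing, 25 at 20%, 29 at 30%.
3. **Compare the arms with a baseline-adjusted mixed model** using the +2 and last samples, with sampling day accounted for, so that patients without a +7 value stay in the analysis. Paired t-tests would drop incomplete pairs.

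The cost of items 1 and 3, and of item 2 with +2 as the named day, is schedule wording, one model and no extra visits. The drawback is that the last sample varies in timing with speed of recovery, possibly by several days: attachment on day 3 with a 7-day stay puts it at +4. The +2 comparison should therefore carry the main marker conclusion, with the last sample as supporting evidence.
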